- Interpretation: If subthreshold CES facilitation occurs at ISI between 2-20 ms, this would support the mechanism of heterosynaptic summation between segmental Ia input and descending corticospinal input¹. If facilitation occurs at ISI between 20-60 ms, this would support the mechanism of sensory cortical facilitation of motor cortex excitability (based on analogous findings using peripheral nerve stimulation^{4,2,3}). Because TMS travels along the same corticospinal and subcortical circuits used during volitional movement, this would also set the basis for using subthreshold CES to facilitate motor

responses during physical training programs (see Aim 2). Subjects with incomplete cervical SCI are expected to have reduced CES-TMS facilitation compared to uninjured subjects (see **Figure 4**).

CES-peripheral nerve interactions:

- Goal: Measure interactions between afferent and efferent cervical nerve roots, segmental interneuronal circuits, orthodromically conducting peripheral sensory fibers, and antidromically conducting peripheral motor fibers.
- Methods: F-wave pulse intensity will be ~110-120% of the intensity that results in maximal compound motor action potential (CMAP). H-reflex pulse intensity will be calibrated to result in H-reflex amplitude ~20-25% of maximal CMAP⁶³. Conditioning CES pulse intensity will be set between 30-175% of motor threshold, delivered within 300 ms of test pulses. For subthreshold conditioning CES, either single or “theta bursts” (3 pulses at 50 Hz)¹⁹ will be delivered. All pulse combinations will be delivered at a rate of 0.1 Hz, in pseudorandom parameter order, until 8 (CES-H combinations) or 25 (CES-F combinations) responses per parameter have been recorded.
- Hypothesis 1.2: Conditioning CES will increase persistence (number of responses per 25 stimuli) of median (APB) and ulnar (FDI) F-responses elicited up to 50 ms later.
- Hypothesis 1.3: Conditioning CES will reduce amplitude of median (FCR) H-responses elicited up to 50 ms later.
- Speculative hypothesis 1.2: Conditioning suprathreshold CES will block spinal motor neuron F-responses delivered up to 10 ms later.

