- Interpretation: These experiments will lead to multiple insights. Through segmental interactions, confirmation of Hypothesis 1.2 would further demonstrate the ability of CES to positively modulate motor neuron excitability, and confirmation of hypothesis 1.3 would indicate the potential for CES to reduce spasticity⁴⁵. Confirmation of speculative hypothesis 1.2 would demonstrate that at high intensity, CES pulses travel via efferent nerve roots and collide with retrogradely traveling F-waves.

Aim 1 data analysis: Peak-to-peak amplitude of all conditioned pulses will be normalized to the amplitude of unconditioned pulses. For each interaction paradigm, analysis of variance (ANOVA) with factors of subject group, stimulus intensity, interstimulus interval, and muscle will be performed. Post hoc pairwise comparisons will be made using Tukey’s method. *Power:* Using a conservative predicted effect size of 0.4 for each interaction paradigm, >80% power will be achieved with a sample size of 10 for each analysis (repeated measure ANOVA) with four factors. 15 subjects in each group (SCI, able-bodied) will undergo testing.

Aim 1 Timeline (Table 2):

Each subject will undergo three testing sessions on separate days, with a minimum of 24 hours and a maximum of two weeks between visits. Per subject, Aim 1 participation would therefore take 3 to 28 days. 30 subjects will be enrolled, resulting in 90 total testing sessions. A conservative projection of completing two testing sessions per week would result in a timeline of 45 weeks or 11-12 months for completing Aim 1.

Aim 2: Determine optimal CES parameters for acutely facilitating concurrent wrist and hand movements.

Volitional limb movements depend on the same corticospinal and spinal motor circuits as those activated by TMS and F-waves. Therefore, since preliminary data shows that subthreshold CES facilitates TMS responses, CES may also be able to facilitate volitional limb movements. The experiments in Aim 2 will shed light on this clinically applicable question.

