Volitional motor tasks: Maximal voluntary contraction (MVC) will be defined as the largest response from 3 attempts at maximal effort prior to testing. Effort will be measured using a customized dynamometer or the root mean square (RMS) of electromyographic activity in the target muscles. The tasks are: opposition between the tips of the thumb and third finger (C8-T1 levels), or wrist extension laterally against a mounted load cell (C6 level). A combined finger opposition/wrist extension task will also be tested. Subjects will be instructed to perform tasks at target effort levels based on real-time display of ongoing EMG or force output.

CES-motor task interaction: Subjects will be given a synchronized audio and visual cue to perform volitional motor tasks at 100%, 50%, or 10-20% of MVC. Volitional tasks will be performed for a maximum of 4 continuous seconds. At least 10 seconds will elapse between each CES/motor task combination. Conditioning CES pulses (or sham pulses at 0% intensity) will be delivered at intensity ranging between 30%-175% of CES resting motor threshold. For subthreshold conditioning CES, either single or “theta bursts” (3 pulses at 50 Hz)¹⁹ will be delivered. Motor task, effort level, and CES parameters will be varied in pseudorandom order, until 8-10 responses per parameter have been recorded.

Aim 2 Outcomes:

- Facilitation: At each muscle, the effect of CES pulses on RMS electromyographic activity over the subsequent 200 ms (in 25 ms bins) will be measured and normalized to the baseline RMS from the preceding 100 ms.
- Silent period: At each muscle, the duration of electromyographic silence is measured from the end of the CES-evoked potential until the resumption of volitional muscle activity (defined as mean rectified EMG amplitude less than or greater than mean baseline activity + 2 standard deviations⁶⁸, respectively).

Hypothesis 2.1: Subthreshold CES will *facilitate* concurrent wrist and hand muscle activation.

Hypothesis 2.2: High-intensity CES will transiently *inhibit* concurrent wrist and hand muscle activation.

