Interpretation: Confirmation of Hypothesis 2.1 would substantiate the predicted findings of Hypotheses 1.1 and 1.2 and our early preliminary data that indicate CES’s ability to positively modulate corticospinal and/or motor neuron excitability. We expect optimal facilitation when subthreshold CES is delivered at closer to motor threshold intensity. We do not know whether the effects will differ depending on intensity of volitional effort, but if so, further experiments could investigate the roles played by peripheral, spinal, and supraspinal components of effort intensity⁶⁹. Furthermore, these experiments would shed light on whether CES modulates ongoing motor neuron activity differently at different spinal levels during level-specific motor tasks (thumb-finger opposition C8-T1, wrist extension C6). Most importantly, confirmation of Hypothesis 2.1 would represent an opportunity to directly translate and test this paradigm for clinical benefit by combining repetitive subthreshold CES with repetitive task-oriented physical exercise training.

If high-intensity CES inhibits concurrent volitional activity as predicted by Hypothesis 2.2, this would be analogous to the ‘cortical silent period’ (CSP) noted when cortical TMS is delivered during volitional contraction^{5,6}. The early phase of CSP (the first 50-75 ms after onset of the cortical motor-evoked potential) is mediated by poorly understood spinal mechanisms⁵. Our observations of the onset and duration of a ‘spinal silent period’ (SSP) in response to CES would shed mechanistic light on this phenomenon.

Aim 2 Data analysis: Rather than peak-to-peak amplitude, the effects of CES on concurrent volitional muscle contraction will be measured using RMS as described above. Repeated-measure ANOVA with factors of subject group, volitional effort intensity, CES intensity, post-stimulus timebin, and muscle will be performed. Post hoc pairwise comparisons will be made using Tukey’s method. Although we can only speculate on the predicted effect size, with use of a conservative effect size of 0.4 for each interaction paradigm, >80% power will be achieved with a sample size of 10 for each analysis (repeated measure ANOVA with five factors). 15 subjects in each group (SCI, able-bodied) will undergo testing.

Aim 2 Timeline:

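### Does the statement of more than 80% power at a sample size of 10 fail because it does not cover the comparison of SCI with able-bodied subjects?

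*Combined protocol and SAP*

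**What the plan says.** Section 3, under Aim 1 data analysis, specifies for each paradigm an "analysis of variance (ANOVA) with factors of subject group, stimulus intensity, interstimulus interval, and muscle will be performed". Responses are first scaled: "Peak-to-peak amplitude of all conditioned pulses will be normalized to the amplitude of unconditioned pulses". The power sentence takes an effect size of 0.4 and says that "for each interaction paradigm, >80% power will be achieved with a sample size of 10 for each analysis (repeated measure ANOVA) with four factors". It is followed by the enrolment: "15 subjects in each group (SCI, able-bodied) will undergo testing".

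Aim 2 Data analysis has the same structure: "Repeated-measure ANOVA with factors of subject group, volitional effort intensity, CES intensity, post-stimulus timebin, and muscle will be performed", with ">80% power will be achieved with a sample size of 10 for each analysis (repeated measure ANOVA with five factors" at the same effect size and again 15 per group. The authors say there that they can only speculate about the effect size.

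One sentence predicts a difference between the groups. It stands under Interpretation in the CES-TMS part of Aim 1: "Subjects with incomplete cervical SCI are expected to have reduced CES-TMS facilitation compared to uninjured subjects".

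The plan does not state the effect-size index, alpha, the correlation among repeated measures, the Aim 1 level counts, whether 10 is a total or a per-group number, or which effect is powered.

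**The concern.** Subject group is the only between-subject factor in either model, and it comes first in both lists. A higher correlation among a subject's repeated measures raises power for within-subject effects and lowers it for the group main effect. A single figure given for each analysis therefore cannot describe both kinds of effect in general, and a sample size of 10 looks far too small to compare two groups.

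What is at stake is how a null group result would be read. Because amplitudes are expressed relative to unconditioned responses, a reduction in SCI of the same size at every interval would appear as a group main effect. A reader who applied the 80% figure to that comparison might take a non-significant result as firmer evidence of no difference than it is.

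**Working it through.** **Inputs from the protocol.** Effect size 0.4; stated sample size 10; enrolled 15 + 15 = 30; one between-subject factor, with three within-subject factors in Aim 1 and four in Aim 2.

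**Assumed inputs, because the plan does not state them.** Cohen's f = 0.4, alpha 0.05, sphericity, and correlation r = 0.5, varied from 0.3 to 0.7.

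**Formulas** (noncentral F; N = total subjects, m = measures per subject):

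- Within-subject: λ = f²Nm/(1 − r), df = (m − 1), (N − 1)(m − 1)
- Group-by-within: same λ, df = (m − 1), (N − 2)(m − 1)
- Group main effect: λ = f²Nm/(1 + (m − 1)r), df = 1, N − 2

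**Step 1: the plan's own figure.** With N = 10, m = 4 and r = 0.5, λ = 0.16 × 10 × 4/0.5 = 12.8.

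- Within-subject, df 3, 27: power 80.6%. With N = 9 it is 75.1%, so 10 is the smallest total that reaches 80% at four levels.
- Group-by-within, df 3, 24: power 79.8%; at five levels it is 86.1%.

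The stated figure is reproduced for within-subject effects with 10 as the total. With 10 per group (N = 20) the within-subject power would be 99.1%, so that reading is not the one that produces 10.

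**Step 2: the group main effect at the stated 10.** With N = 10, m = 4 and r = 0.5, λ = 6.4/2.5 = 2.56, df 1, 8: power 29.2%. For m from 1 to 100 the range is 20-35% if 10 is the total and 40-66% if it is per group. At r = 0.5 the 80% does not reach this effect on either reading.

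**Step 3: how many cells the designs have.**

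- Aim 1: three within-subject factors with at least two levels each give at least 2 × 2 × 2 = 8. The H-reflex is recorded in one muscle, so that analysis could have as few as 4.
- Aim 2: 200 ms in 25 ms bins gives 8 bins. Subjects also "perform volitional motor tasks at 100%, 50%, or 10-20% of MVC", which is 3 effort levels. So there are at least 8 × 3 = 24 cells before CES intensity and muscle are counted.

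**Step 4: the group main effect at the enrolled 30.** The numerator of λ is 0.16 × 30 × m = 4.8m. At r = 0.5:

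- m = 8: λ = 38.4/4.5 = 8.53
- m = 24: λ = 115.2/12.5 = 9.22
- m = 100: λ = 480/50.5 = 9.50

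Power, with df 1, 28:

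| r | m = 4 | m = 8 | m = 24 | m = 100 |
|---|---|---|---|---|
| 0.3 | 86.6% | 92.5% | 95.8% | 96.8% |
| 0.5 | 76.3% | 80.5% | 83.4% | 84.5% |
| 0.6 | 71.5% | 74.6% | 76.8% | 77.7% |
| 0.7 | 67.1% | 69.3% | 70.7% | 71.3% |

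The highest correlation that still gives 80% is about 0.50 at 8 cells, 0.55 at 24 and 0.56 at 100.

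The formula gives 56.2% at m = 1. That is the power for a single measure. It is not the power after averaging a subject's cells: under this model the group test on m cells is the test on their average, so averaging 8 cells already gives 80.5%.

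**Step 5: within-subject and group-by-within effects at the enrolled 30.** At r = 0.3 power is 94.7% with two levels and 98.3% with three. At r = 0.5 it is 98.8% or more. If sphericity fails badly (epsilon 0.5, three levels, r = 0.3), within-subject power is 87.3%.

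**The case for a change.** The strongest case for a change is that no single figure can cover two effects that respond to the correlation in opposite directions, and that this holds whatever inputs are assumed. The study enrols two equal groups, names group as a factor in both Aims and predicts a direction. At 8 cells and correlation 0.5 the margin over 80% is half a point. At correlation 0.7, adding cells never brings the group effect above about 71%. Separate figures would cost only a few lines of text.

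Two parts of this stand. The power text should ideally have named its inputs and target effect, and a sample size of 10 does not support the group main effect at correlation 0.5.

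The rest is weaker. The plan ties the effect size to the interaction paradigms and nowhere claims 80% for the group main effect. Hypotheses 1.1 to 1.3 and 2.1 to 2.2 all concern what CES does within a subject. The SCI expectation is an interpretive remark. The same paragraph places facilitation in particular windows (2-20 or 20-60 ms) out of intervals up to 300 ms, so a reduction in SCI would most naturally appear as group-by-interval, which is well powered. A shortfall needs both a uniform reduction and a correlation above about 0.50-0.56. The four-cell case fits at most the H-reflex analysis, for which no group difference is predicted; none is predicted in Aim 2 either. The answer also depends on the effect-size index: if 0.4 is partial eta-squared (f = 0.82), the group effect has 82% even at a total of 10 with four measures and correlation 0.5.

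**Conclusion.** The concern does not call for a change. The stated power is reproduced at a total of 10 for the within-subject CES effects that the numbered hypotheses address, and at the enrolled 30 those effects have about 95% or more under sphericity with correlation 0.3 or higher. The group main effect at 15 + 15 is borderline rather than shown to be inadequate: 80-85% at correlation 0.5 with 8-100 cells, 93-97% at 0.3 and 69-71% at 0.7. All of this assumes f = 0.4 and alpha 0.05, which the plan does not confirm.

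What remains is missing detail in a planning paragraph. Supplying it would leave the enrolment, the models and the post hoc comparisons as they are. An analyst who finds no group difference can judge it from its estimate and confidence interval, which show the precision achieved whatever the planning text said.

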Potential participants will be encouraged to ask questions throughout the process. Potential participants will be informed of their right to withdraw at any time and that choosing to not participate will not infringe on any of their regular VA benefits or medical care. Once he/she has no further questions and the study team is confident that the potential participant fully understands the protocol and its risks, then the participant will be asked whether he or she is willing to sign the ICF.

Procedures:

General: All procedures are performed in a seated position with elbows at roughly 90 degrees and hands resting on a pillow in pronated position. Electrophysiological measurements are made using the dominant or stronger affected arm. Safety (blood pressure, heart rate, pulse oxygenation, peak expiratory flow rate, and structured symptom questionnaire) and tolerability are closely monitored throughout all experiments (see Human Subjects section).

Electromyography (EMG): EMG is recorded using surface sensors with 300x preamplification, 15-2,000 Hz bandwidth, and internal grounding (Motion Lab Systems). EMG input is collected at a sample rate of 5,000 Hz via digital acquisition board and customized LabVIEW software (National Instruments). Muscles recorded may include abductor pollicis brevis (APB), abductor digiti minimi (ADM), first dorsal interosseous (FDI), flexor carpi radialis (FCR), extensor carpi radialis (ECR), and/or biceps brachii.

TMS: TMS is performed using a MagPro X100 stimulator (MagVenture). The hand motor cortex ‘hotspot’ is found while monitoring EMG motor response. Location of the hotspot and all subsequent TMS stimuli are tracked using a neural navigation system (Brainsight). Resting motor threshold is determined by delivering pulses with increasing intensity until motor responses of $\geq 50\text{ }\square\text{V}$ are observed in the APB or FDI muscle in at least 5 out of 10 stimuli.

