CES: CES is performed using two DS7A nerve stimulators or a dual DS8R stimulator (Digitimer) linked to deliver biphasic pulses (1 ms each phase; cathodal first). The cathode is a 5x10 cm surface electrode (Natus) placed longitudinally with the top edge ~2.5 cm caudal to the C7 spinous process (~T1-T3 vertebral levels posteriorly). The 5 x 10 cm anode is placed horizontally over the thyroid cartilage, corresponding to the C4-C5 levels anteriorly. Two 5x10 cm common ground electrodes are placed over the distal clavicles. Stimulus intensity ranges from 0-80 mA. Motor threshold is determined analogously to the method used in TMS. Blood pressure, heart rate, pulse oximetry, and peak expiratory flow rate are monitored every three minutes.

Peripheral nerve stimulation: Stimulation is delivered using a DS7A or a DS8R nerve stimulator and dual surface electrodes (20 mm apart). M-wave and F-reflex responses are triggered over the median and ulnar

nerves at the wrist, recording over the APB and FDI muscles, respectively. F-wave pulse intensity is ~110-120% of the intensity that results in maximal compound motor action potential (CMAP). H-reflex responses are triggered over the median nerve at the elbow, recording over the FCR muscle. H-reflex pulse intensity will be calibrated to result in H-reflex amplitude ~20-25% of maximal CMAP⁶³. Pulse width is 0.2 ms for M/F wave stimulation and 1.0 ms for H-reflex stimulation.

Timing: Peripheral motor conduction time is calculated using F-wave and M-wave latencies using the formula $(\text{Latency}_M + \text{Latency}_F - 1) \div 2$ ⁶⁴. Central motor conduction time is calculated as the TMS-evoked potential latency minus the peripheral conduction time. These values are used to precisely synchronize arriving TMS, CES, and peripheral pulses at cervical motor neurons in the relevant experiments.

Replication: For Aim 1, testing will occur over three sessions. For Aim 2, testing will occur over two sessions. This will allow confirmation of key intensity and timing parameters defined for each subject over different sessions, improving reliability of the findings.

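### The Aim 2 RMS outcome starts at the CES pulse with no offset, so its early bins mix any CES-evoked potential with volitional EMG, most clearly above motor threshold

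*Combined protocol and SAP*

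**What the plan says.** All of this is in section 3 of the combined protocol and SAP.

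- **Aim 2 Outcomes, Facilitation.** For every recorded muscle, "the effect of CES pulses on RMS electromyographic activity over the subsequent 200 ms (in 25 ms bins) will be measured". That makes eight bins, each divided by RMS from the 100 ms before the pulse. No blanking interval, offset or exclusion of the evoked response is given.
- **Aim 2 Outcomes, Silent period.** Here "the duration of electromyographic silence is measured from the end of the CES-evoked potential", so this outcome does step past the evoked response.
- **CES-motor task interaction.** "Conditioning CES pulses (or sham pulses at 0% intensity) will be delivered at intensity ranging between 30%-175% of CES resting motor threshold". Subthreshold CES may be a single pulse or a burst of "3 pulses at 50 Hz".
- **Procedures, TMS and CES.** CES threshold follows the TMS rule: the lowest intensity at which responses of the required size "are observed in the APB or FDI muscle in at least 5 out of 10 stimuli", measured at rest. Each biphasic pulse has two 1 ms phases. The EMG paragraph gives bandwidth and sampling rate (5,000 Hz) but no artefact handling.
- **Aim 2 Data analysis.** "the effects of CES on concurrent volitional muscle contraction will be measured using RMS as described above". The model is a repeated-measures ANOVA with post-stimulus time bin among its five factors, followed by Tukey comparisons. No analysis is given for silent-period duration, and no rule says which bins decide H2.1 or H2.2.

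**The concern.** The numerator of the facilitation ratio covers the interval in which a direct CES response arrives; the denominator does not. Sham at 0% intensity has neither pulse nor response, so comparison with sham does not remove the difference. A directly evoked response is therefore counted as a change in volitional activity.

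For H2.2, early bins can rise above baseline while the muscle is otherwise silent, and a CES-intensity effect averaged over bins can be pulled the same way. For H2.1, subthreshold does not mean response-free: just below threshold, up to 4 of 10 stimuli may respond at rest. The Aim 2 interpretation also expects the best facilitation close to threshold, where such responses are most likely. The plan would carry a positive H2.1 forward to clinical testing with exercise, so it matters whether the effect reflects volitional drive or a direct response.

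**Working it through.** The plan states no figure for this outcome, so there is none to reproduce. The check models the outcome as written.

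**From the plan:** eight 25 ms bins, 2 ms per pulse, burst pulses at 0, 20 and 40 ms (50 Hz).

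**Assumed, because the plan gives no values:** an evoked potential lasting 10 ms, sinusoidal, with peak-to-peak size k times baseline RMS; latency 8, 14 or 20 ms; artefact lasting 2 ms with RMS a times baseline; true silence of 50, 75 or 100 ms from the end of the evoked potential. Baseline RMS is set to 1 and powers add.

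**1. Where the contamination falls.** For a single pulse, artefact is in bin 1. The evoked potential is in bin 1, or in bins 1-2 at 20 ms latency. For a burst timed from its first pulse, artefact is in bins 1-2 and evoked potentials are in bins 1-3.

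**2. No true effect, evoked potential within one bin.** The sinusoid has power k²/8 for 10 of 25 ms, so the bin ratio is √(1 + (10/25)·k²/8) = √(1 + 0.05k²). This gives 1.10 at k = 2, 1.50 at k = 5 and 2.45 at k = 10.

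**3. No true effect, artefact only.** The bin 1 ratio is √(1 + (2/25)·a²): 1.15 at a = 2, 1.73 at a = 5 and 3.00 at a = 10.

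**4. Suprathreshold pulse, 75 ms of true silence, 14 ms latency.** The evoked potential runs from 14 to 24 ms and silence from 24 to 99 ms. Bin 1 is √(0.96 + 0.05k²), bins 2-3 are 0, bin 4 is √(1/25) = 0.20, and bins 5-8 are 1.

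| k | Bin 1 | Bins 2-3 | Bin 4 | Mean of 8 bins |
|---|---|---|---|---|
| 5 | 1.49 | 0 | 0.20 | 0.71 |
| 10 | 2.44 | 0 | 0.20 | 0.83 |
| 20 | 4.58 | 0 | 0.20 | 1.10 |
| 50 | 11.22 | 0 | 0.20 | 1.93 |

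The mean equals 1 when bin 1 = 8 − 4 − 0.20 = 3.80, that is k = √((3.80² − 0.96)/0.05) = 16.4. Break-even k for the eight-bin mean, by latency:

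| Silence | 8 ms | 14 ms | 20 ms |
|---|---|---|---|
| 50 ms | 10.4 | 11.7 | 8.6 |
| 75 ms | 15.1 | 16.4 | 12.0 |
| 100 ms | 19.6 | 21.0 | 15.4 |

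Bin 1 alone exceeds baseline at k above 2.4 (8 ms latency) or 0.9 (14 ms), and at any k at 20 ms. At 20 ms latency and k = 10, bin 2 also reads 1.64.

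**5. Near-threshold pulse, response in 4 of 10 trials, no other effect.** At k = 5, bin 1 averages 0.4 × 1.50 + 0.6 × 1 = 1.20, and the eight-bin mean is (1.20 + 7)/8 = 1.025. At k = 10, bin 1 is 0.4 × 2.45 + 0.6 = 1.58 and the mean is (1.58 + 7)/8 = 1.07.

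**6. Window started after the evoked potential.** With no effect every bin is 1.00. With 75 ms of silence the first three bins are 0 and the eight-bin mean is 5/8 = 0.625. The sign is right whatever k is.

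**The case against.** The strongest reply is that the plan is not blind to time. Time bin is a factor with post hoc comparisons, H2.2 predicts a transient effect, and in the first table above bins 2-3 show complete inhibition whatever the value of k. H2.2 also has a silent-period outcome that begins after the evoked potential. A reader might infer that H2.2 will come out with the wrong sign; the documents do not support that. What remains is that the early bins are biased, the CES-intensity main effect averages over all bins, no bins are named as decisive, and the silent period has no analysis. Its criterion also needs its own check, because activity below baseline mean plus 2 SD includes ordinary baseline activity.

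The sizes are assumptions too. A striking case, one bin at 10 times baseline and three silent bins, gives (10 + 0 + 4)/8 = 1.75, but it needs k of about 44. At k = 5 the eight-bin mean has the right sign. Stronger contraction raises baseline EMG and lowers k; the 10-20% effort level does the opposite. The documents give no EMG amplitudes.

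For H2.1, a reader might infer that direct responses alone could account for any facilitation found. The threshold rule supports at most a minority of responding trials at rest. Moreover, early EMG may be part of what is sought: the Aim 1 interpretation places heterosynaptic summation at 2-20 ms, and the Aim 2 interpretation speaks of corticospinal and/or motor neuron excitability. Discarding the early bins would therefore be wrong. This objection stands and shapes the fix.

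Lastly, the documents report no artefact at the recording sites, and part of the CES preliminary-data section was not available to read, so a processing note there cannot be ruled out. Artefact is a possibility to provide for, not a finding.

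**Conclusion.** The concern holds in a limited form. Applied as written, the RMS rule counts a CES-evoked potential as change in volitional activity, in bins 1-2 for a single pulse and up to bin 3 for a burst timed from its first pulse. The plan recognises the evoked potential in the silent-period definition but not in the one outcome for which it specifies an analysis.

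Above threshold, bin 1 can show apparent facilitation during true inhibition. The bin-averaged effect changes sign only for a large evoked potential: k of about 12-16 for 75 ms of silence, or 9-21 over 50-100 ms. Near threshold the bias is smaller, about 1.20 in bin 1 for k = 5 in 4 of 10 trials. That contraction would make responses more frequent than at rest is plausible, but the documents do not say so. All sizes rest on the assumed shape, duration and latency; where the contamination falls depends mainly on latency and on time zero for bursts. This should be settled before analysis. It does not invalidate the later bins or the silent-period measure.

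**What to change.** 1. Define time zero as the last pulse of a single or burst stimulus, with the same clock in sham trials. Keep the 100 ms baseline before the first pulse; otherwise it would contain the burst pulses at −40 and −20 ms.
2. Blank any stimulus artefact over a stated interval, identically in all trials.
3. For each subject and muscle, fix an early window from that subject's suprathreshold CES-evoked potential and apply it unchanged to sham, subthreshold and suprathreshold trials. A fixed window is needed because subthreshold trials without a response have no end of evoked potential to mark. Add a margin, since the preliminary data put near-threshold latency up to about 3-5 ms beyond peripheral motor conduction time.
4. Report RMS in the early window as its own outcome, and cut the 25 ms bins from the end of that window.
5. Test H2.2 on the later bins and on silent-period duration, with the analysis of the latter written down.
6. For H2.1, report early-window and later-window effects separately. Do not describe an effect confined to the early window as facilitation of volitional drive.

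The cost is signal-processing and SAP wording on EMG already recorded at 5,000 Hz, with no added stimulation. The downside is that short-latency summation cannot be separated from a direct evoked response, so it has to be interpreted on its own.
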